6.2.4 Blood DNA bacteria

Up to 10mL blood will be collected in a 3mL K₂EDTA Whole Blood Collection Tube manufactured by BD (BD Product number: 367856). Isolation of bacterial DNA from blood is obtained by adding 1.5 ml of whole blood to 6 ml of 0.17 M ammonium chloride. The sample are incubated for 20 minutes at 37° C and centrifuged for 10 minutes at 10 000 rpm. The supernatant is removed and the precipitate is suspended in 100 μ l of solution of lysozyme (2 mg/ml) and lysostaphin (0.2 mg/ml) in PBS buffer. Sample are then transferred to Eppendorf tubes with glass beads (700-1100 μ m) and subjected to mechanical disruption for 20 seconds at a speed of 4.0 m/s. Again, sample are incubated for 30 minutes at 37° C and centrifuged for 10 minutes at 12 000 rpm.

6.2.5 Stool collection

Fecal samples will be collected from patients at baseline, and months 1 to 12 inclusive prior to receiving their scheduled FMTs. To collect the stool samples the participants will collect a piece of visibly soiled toilet paper and place it into a DNA-free bag. The bag will be transported to the Lawson Health Research Institute at St. Joseph’s Hospital and stored at -80 °C until the time of DNA extraction when all samples are collected. DNA will be extracted using the MO BIO Powersoil 96-well soil isolation kits, as adapted for the Human Microbiome Project. After DNA extraction, the V4 region of the 16S rRNA gene will be amplified using validated bar-coded PCR primer sets. After amplification, the samples will be sent for Illumina MiSeq sequencing (London Regional Genomics Centre). The reads generated from sequencing will be demultiplexed, taxonomically assigned by BLAST, and analyzed using the program R. Microbiome analysis will follow the protocol as described in Bisanz et al.⁴ A principal component analysis will be conducted and ALDEx2 tests will be performed to determine what the main differences in bacterial composition are between samples. The microbial composition at baseline will be compared to the other time points to determine how long it takes for the recipient to revert to their original microbiota. The donor microbiota will also be compared to each time point to determine how similar the patient’s bacterial composition is to the donors after transplant.

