In the event of early termination, a visit will be performed whenever possible, including a final blood sample and all end of treatment assessments that should be completed as soon as possible. All patients with at least 1 week of treatment will be

eligible for analysis.

Number of Patients:

A maximum of 40 patients will be enrolled in intervention part of this study and randomized 1:1 into one of the two groups [20 patients per group] using an internet based randomizer software [<https://www.randomizer.org/>]. We may screen up to an extra 10 patients to compensate for possible drop outs, withdraw consent or those who discontinued for any other reason.

We will also recruit up to 10 healthy volunteers to provide a blood sample [1 tube, 5 ml] to serve as a reference arm for the cytokine analysis. This reference group will be seen only once and will not participate in any other study activities.

Consequently, the total number of participants in this study will be n=50.

Inclusion criteria for patients:

1. Have a confirmed diagnosis of relapsing MS defined by the 2010 Revised McDonald Criteria for the Diagnosis of Multiple Sclerosis¹
2. Have a baseline Expanded Disability Status Scale (EDSS) ≤ 7.0
3. Age equal or older than 18 years of age
4. Be able to attend all clinic appointments without interruption
5. Be proficient in English
6. Be willing and able to give written informed consent
7. Negative blood pregnancy test at screening

Exclusion criteria for patients

1. Not meeting all of the above inclusion criteria
2. Pregnancy [current or planned for the near future] or breastfeeding
3. All qualified patients will not be currently or recently [90 days] treated with immunosuppressive therapy [i.e. chemotherapy] or high dose corticosteroids [i.e. 1g of prednisone or greater or equivalent]. Immune-Modulatory therapies are allowed as per standard of care.
4. Ongoing use of antibiotics
5. Presence of a chronic intestinal disease e.g. celiac, mal-absorption, colonic tumor
6. Concomitant inflammatory diseases
7. Standard of care exclusions for MRI scans as per LHSC standards

Healthy controls Selection:

1. Age equal or older than 18
2. Written informed consent
3. Self reportedly “healthy”, in particular not having a history of any disease or

disorder, or any treatment ever for such [ie lupus, cancer, etc], that in the opinion of the PI could be possibly related to changes in the immune system that would alter the results of a cytokine in blood analysis.

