Patients will also undergo a contrast-enhanced brain MRI scan at Robarts Institute in London Ontario. Other baseline assessments (prior to the first dose of therapy) include an EDSS, pregnancy test (if applicable), and physical exam. Blood samples are also taken at this visit in order to establish a baseline for routine chemistry/hematology. After all this assessments FMT will be performed by a trained nurse via a rectal enema

Patients will return to the clinic for visit 4 weeks after the first FMT. Another stool sample to evaluate the microbial before the second FMT will be collected. Also peripheral blood samples for cytokines and blood bacterial DNA analysis. This same routine procedure will be

repeated at month 2, 3, 4 and 5 for the early intervention group and at month 6, 7, 8, 9, 10 and 11 for the late intervention group. Both groups will come to clinic at baseline and month 1 to 12 inclusive, even if they are not receiving FMT. During all visits, a stool sample, a cytokine sample and a blood DNA bacteria sample will be collected. It is worth mentioning that at 6 and 12 months another urine analysis will be done to evaluate gut permeability and MRI study at Robarts Institute, London, Ontario for safety assessment will be performed for both groups.

Another safety assessment in each visit after FMT is to review of any adverse events that may have occurred. All patients receiving at least 1 week of treatment will be eligible for analysis.

Table 1. Early Intervention Group Schedule

[figure not shown]
Study Months	Pre-Visit	Baseline	Month 1	Month 2	Month 3	Month 4	Month 5	Month 6	Month 7	Month 8	Month 9	Month 10	Month 11	Month 12
Visit Duration	1.5hours	1.5hours	1.5hours	1.5hours	1.5hours	1.5hours	1.5hours	45min	45min	45min	45min	45min	45min	45min
Informed Consent Form	X													
Fecal Transplantation		X	X	X	X	X	X							
Height		X												
Weight, Vital Signs		X	X	X	X	X	X	X	X	X	X	X	X	X
Stool Sample		X	X	X	X	X	X	X	X	X	X	X	X	X
Urine: Gut Permeability		X						X						X
Circulating Cytokine Levels and Blood DNA		X	X	X	X	X	X	X	X	X	X	X	X	X
MRI		X						X						X
Routine Hematology and Urinalysis		X	X	X	X	X	X	X	X	X	X	X	X	X
Physical Exam/ EDSS		X	X	X	X	X	X	X	X	X	X	X	X	X

Table 2. Late Intervention Group Schedule

Study Months	Pre-Visit	Baseline	Month 1	Month 2	Month 3	Month 4	Month 5	Month 6	Month 7	Month 8	Month 9	Month 10	Month 11	Month 12

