7.0 ASSESSMENT OF EFFICACY

As this study is an immunological study, the following efficacy outcomes will be evaluated:

- Changes in peripheral blood cytokines within RMS patients between baseline and months 1 to 12 inclusive, for both groups. Luminex kit will be used.
- Changes on microbiome after FMT by analyzing the gut bacterial composition through stool analysis and blood bacteria DNA at baseline, and months 1 to 12 inclusive for both groups.
- Gut permeability through urine analysis at baseline, 6 and 12 months for both groups.

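### Section 6.2.5 tests stool taxa without a stated early v late comparison, pairing, patient-level unit or false-discovery control, and does not say whether the mixed ANOVA of section 9.3 applies

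*Combined protocol and SAP*

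**What the plan says.** Stool is taken at every visit in both groups. Section 4 says: "During all visits, a stool sample, a cytokine sample and a blood DNA bacteria sample will be collected". Section 6.2.5 fixes the timing: "Fecal samples will be collected from patients at baseline, and months 1 to 12 inclusive prior to receiving their scheduled FMTs". The synopsis has patients "randomized 1:1 into one of the two groups [20 patients per group"].

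Section 7.0 lists as an efficacy outcome "Changes on microbiome after FMT by analyzing the gut bacterial composition through stool analysis", for both groups at baseline and months 1 to 12.

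The analysis is in section 6.2.5. After a principal component analysis, "ALDEx2 tests will be performed to determine what the main differences in bacterial composition are between samples". Two contrasts follow. In the first, "The microbial composition at baseline will be compared to the other time points", with the purpose "to determine how long it takes for the recipient to revert to their original microbiota". In the second, "The donor microbiota will also be compared to each time point", to judge how close the patient's flora comes to the donor's. The rest is deferred to a cited paper.

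Section 9.3, headed Biomarkers, plans a mixed-design ANOVA with two independent groups and repeated measures. It mentions neither taxa nor ALDEx2.

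**The concern.** The trial randomises patients to early or late FMT, so for the first six months it has a concurrent untreated group with monthly stools. The microbiome section never says that this group will be used as a control. A before-after contrast credits FMT with anything that moves stool composition over the same months, such as diet, season, changes of medication or laboratory drift.

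The section also does not say what the unit of analysis is when each patient gives 13 stools, whether baseline contrasts are paired, or how many taxa are tested under what error control. These choices decide whether the test is valid, too weak or too liberal.

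The results are meant to be used. Section 4.1 expects the data to be tested for significance, and section 11.4.2 looks ahead to choosing organisms to supplement or remove in later studies. A taxon wrongly linked to FMT, or a false conclusion about how long the transplant persists, would carry forward.

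**Working it through.** **No planned figure to reproduce.** The documents give no power, error rate or number of taxa for the microbiome analysis.

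**Inputs from the documents.** 40 patients, 20 per group (synopsis). Stools per patient: 1 + 12 = 13, so 40 x 13 = 520 if complete (sections 4 and 6.2.5). The late group's first FMT is at month 6 (Table 2), and stool is taken before FMT (section 6.2.5). Its stools from baseline through month 6 are therefore all untreated. The early group's stools at months 1-6 all follow at least one FMT (Table 1).

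**Assumptions.** The ICC of a taxon is not in the documents; 0.3, 0.5 and 0.7 are shown. The model is one normally distributed taxon with equal correlation between any two stools of a patient and no true effect. Each setting used 20,000 simulated trials and two-sided 5% t-tests. ALDEx2 itself was not run.

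**A. Baseline v a later time point, the contrast that 6.2.5 names.** An unpaired test takes the variance of the mean difference as 2 x variance / n. The true value is that times (1 - ICC). The standard error used is thus too large by 1/sqrt(1 - ICC), which is 1.20, 1.41 and 1.83 at ICC 0.3, 0.5 and 0.7. At ICC 0.3 the true error is 2 x [1 - Phi(1.96/sqrt(0.7))] = 2 x [1 - Phi(2.34)] = 1.9%.

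**B. Early v late over months 1-6 with every stool counted as independent (120 v 120).** The plan does not state this test. The design effect is DE = 1 + (6 - 1) x ICC = 2.5, 3.5 and 4.5. The true error is 2 x [1 - Phi(1.96/sqrt(DE))] = 21.5%, 29.5% and 35.6%.

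| True error of a nominal 5% test (simulated) | ICC 0.3 | ICC 0.5 | ICC 0.7 |
|---|---|---|---|
| Baseline v month 6, unpaired | 1.9% | 0.7% | 0.07% |
| Baseline v month 6, paired | 4.9% | 5.3% | 5.0% |
| Baseline v all later stools pooled, unpaired | 2.0% | 0.7% | 0.06% |
| Early v late, months 1-6, stools pooled | 21.8% | 30.0% | 36.5% |
| Early v late, one mean per patient, months 1-6 | 4.9% | 4.8% | 5.1% |
| All stools before v after first FMT, pooled | 13.0% | 18.0% | 22.6% |

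The direction depends on the contrast. Ignoring the patient makes the named baseline contrast conservative. It inflates error only where repeated stools are pooled in a contrast that is wholly or partly between patients, as in the fourth and last rows. Pairing, or one summary per patient, brings the error back to about 5%.

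**C. Multiplicity.** The number of taxa is not stated. As an illustration, 100 null taxa each tested correctly at 5% would give 100 x 0.05 = 5 false positives on average.

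**The case against.** A reader might infer something stronger: that the plan treats the 520 stools as independent and will declare chance taxa to be FMT effects. The documents do not support that. They are silent on the unit of analysis, and speaking of differences between samples says what is compared, not what is counted as independent. Compared one time point at a time, each patient contributes one stool per time point, so nothing is pooled. For that contrast, ignoring pairing lowers the error rate. Pooling all 13 stools between arms would not be an FMT contrast at all, because each arm has a treated and an untreated half, so no error rate for it belongs here.

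Three further defences deserve an answer.

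- *Section 9.3 may already cover taxa.* It has the group factor and the repeated measures, and transformed abundances could be entered in it. This stands as a possible reading. But it names no taxa, the protocol mostly uses the word biomarker for cytokines, and 6.2.5 names a different method without linking the two.
- *The cited paper may settle the details.* It cannot be seen here. As printed, the citation carries number 4, which in the reference list is a general overview of multiple sclerosis, and the named source is not listed. A reader of the protocol cannot recover the missing choices from it.
- *The aims in 6.2.5 are mainly descriptive and the study is exploratory.* This is fair: stool composition is in neither the primary nor the secondary outcomes of section 3. It is nevertheless an efficacy outcome in section 7.0 and an evaluation criterion in the synopsis.

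**Conclusion.** The point holds as a gap in specification with a definite consequence. Followed as written, 6.2.5 gives an uncontrolled before-after contrast although a randomised untreated group is available for the same six months, and so cannot separate FMT from drift.

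The size of the remaining problem depends on choices that the plan leaves open. An unpaired baseline contrast would have a true error of about 1.9% to 0.07% at ICC 0.3 to 0.7, with a matching loss of power. That matters most for the time-to-reversion aim, where a test too weak to find a difference can be read as a return to baseline. The inflation to about 22%, 30% and 36% applies only if months 1-6 stools were pooled between arms, which the plan does not say it will do.

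The percentages rest on assumed ICCs and a simple normal model. The missing control comparison does not depend on them.

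**What to change.** Amend section 6.2.5 as follows.

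1. Make the patient the unit of analysis.
2. For the FMT effect, compare early with late (still untreated) patients on each taxon's centred-log-ratio change from baseline to the patient's mean over months 1-6. An equivalent group-by-time model with a patient random effect would also serve.
3. Apply Benjamini-Hochberg control over the taxa tested.
4. Use paired tests for baseline v each later time point, and report time to reversion from these.
5. Keep the principal component analysis as a display. If permutation tests accompany it, permute whole patients for early v late, because group never changes within a patient, and permute within patient only for time contrasts.
6. State whether section 9.3 applies to taxa and how it relates to ALDEx2, and correct the citation.

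The cost is protocol and SAP wording and a little more analysis work. All the stools are already scheduled. The between-group test may flag fewer taxa than a before-after test. One limit remains: after month 6 the late group is itself on FMT, so persistence in the early group beyond that point has no untreated concurrent control and should be reported as descriptive.

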6.2.6 Urine analysis for gut permeability

Patients will be instructed not to consume alcohol on the day of the test or 5 days previously. Also, to eat supper before 6:00 pm, and then no food or drink is to be consumed after this time. At bedtime, patients will be advised to empty bladder and discard urine.

A packet containing sugar (lactulose) and mannitol will be provided. Patients will be instructed to empty the packet into a glass of water according to the table below.

Weight	Lactulose	Mannitol	Sucrose	Tap water
45kg-up	5 grams	2.0 grams	100 grams	450ml

Throughout the night and first thing in the morning, all urine must be collected and brought to St Joseph’s Health Care.

6.3 Sample Size analysis

It was assumed that the acceptable Type I error will be 0.05 and power will be 0.8. Moderate effect size effect is expected. This is a study of a kind that has never been done before in this population. From similar studies in other populations or other interventions on a similar population, a 40% change in cytokine levels (ie TGFbeta1) analysis is expected, as reported on other cytokine study with no pharmacological intervention, such as vitamin D supplementation⁷³.

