4.2 Duration of therapy and study

Patients will be screened prior to starting treatment with FMT and randomized between 2 groups. One, early intervention group, will receive FMT for the first 6 months and the other will be a control group treated as standard only. After 6 months, the early intervention will not receive the transplantation anymore and the control group will receive FMT for the remaining 6 months. Study drug will be administered for a period of 6 months for each group total.

Patients may withdraw consent at any time. Study drug may be discontinued at any time by the investigator if doing so is deemed to be in the best interest of the patient. However, the patient should be encouraged to continue in the study for safety follow-up.

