6.2.1 Screening, Enrolment and Baseline

An informed consent form must be signed prior to initiating any procedures or evaluations for the purpose of the study (**Appendix B**). After the informed consent form has been signed patients will be randomized to receive FMT for the first 6 months of the study or to be a standard per treatment control group that will received treatment at the last 6 months of the study.

The following evaluations at baseline visit and prior to FMT will be performed in both groups:

- Medical history;
- Vital signs (including pulse, respiration rate, blood pressure and temperature);
- Physical Exam (including weight in kg);
- Concomitant medications;
- Dietary history;

- Expanded Disability Status Score (EDSS);
- Blood samples will be taken for haematology (including haemoglobin, red blood cell count, white blood cell count, differential and platelets);
- Blood samples will be taken for serum chemistry (sodium, potassium, chloride, uric acid, creatinine, blood urea nitrogen, total protein, calcium, albumin, total bilirubin, AST, ALT, alkaline phosphatase, glucose);
- Blood sample for multiplex cytokine profiling (includes pro-inflammatory (IL-6, IL-15, IL-17, GM-CSF, TNF α) and anti-inflammatory (IL-4, IL-10 and IL-14) cytokines).
- Clean catch, mid-stream urine for urinalysis and micro analysis (including pH, protein, glucose, ketones, nitrites, leukocyte esterase, RBCs, WBCs) and gut permeability;
- Blood sample for blood bacterial DNA
- Head MRI as baseline

After evaluation, the FMT via rectal enema will be performed by a RN in each visit.

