6.2.3 Peripheral blood cytokines levels

Cytokine levels will be measured as previously described⁷². Peripheral blood will be collected into EDTA blood collection tubes ensuring complete mixing with anticoagulant to avoid clotting. Within 60 minutes of blood collection samples will be spun for 10 minutes at 4500xg. The plasma will be collected and aliquoted into cryovials. All samples will be collected and stored at -80°C before the plasma is measured for 25 immunological cytokines using a luminex-based multiplexed immunoassay. The Human Th17 Magnetic bead panel (HTH17MAG-14K, Millipore) will be used in this study to detect changes in Interleukin 1 β (IL-1 β), IL-2, IL-4, IL-5, IL-6, IL-9, IL-10, IL-12p70, IL-13, IL-15, IL-17A, IL-17E/IL-25, IL-17F, IL-21, IL-22, IL-23, IL-27, IL-28A, IL-31, IL-33, granulocyte macrophage colony stimulating factor (GM-CSF), interferon γ (IFN γ), macrophage inflammatory protein 3 α (MIP-3 α), tumour necrosis factor α (TNF α) and TNF β . Plasma samples will be run in duplicate and assays will be standardized as per product specifications. Plasma cytokine levels in healthy controls will be compared to levels in MS patients at all time points. Moreover, cytokine levels of MS patients at baseline (D0) will be compared to levels at 12 months to determine whether intervention (FMT) had an effect on pro- and anti-inflammatory cytokine levels.

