9. STATISTICAL ANALYSIS

9.1 Sample Size Selection

This is an exploratory proof of concept immunological study. As such the number of patients in each treatment group was arbitrarily chosen in lieu of a convenience sampling for this type of study.

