9.3 Biomarkers

We will analyze mean differences between two independent groups whilst subjecting participants to repeated measures overtime to assess variability between- and within-subjects variable. Therefore, we will use the mixed-design ANOVA model.

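### Section 6.3 states 80% power without a derivation, section 9.1 calls the group size arbitrary, and the only numeric planning effect is tied to a cytokine that is not measured

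*Combined protocol and SAP*

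**What the plan says.** Section 6.3, headed as the sample size analysis, states: "It was assumed that the acceptable Type I error will be 0.05 and power will be 0.8. Moderate effect size effect is expected". It adds that "a 40% change in cytokine levels (ie TGFbeta1) analysis is expected", citing a vitamin D supplementation study as reference 73. It gives no N, test, sidedness, SD or CV, correlation, direction of change or dropout rate.

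Section 9.1 calls the study exploratory proof of concept and says "the number of patients in each treatment group was arbitrarily chosen in lieu of a convenience sampling for this type of study". The figure of 40 patients, 20 per group, comes from the synopsis and section 4.

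Two analyses of the cytokines in the trial patients are described elsewhere. Section 9.3 says "We will analyze mean differences between two independent groups whilst subjecting participants to repeated measures overtime" and names a mixed-design ANOVA, without saying which term is the test of interest. Section 6.2.3 compares patients' baseline levels with those at 12 months to judge whether FMT had an effect. Section 6.3 refers to neither.

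On what is measured, section 6.2.3 says "The Human Th17 Magnetic bead panel (HTH17MAG-14K, Millipore) will be used in this study to detect changes in" 25 listed analytes, and the synopsis repeats the list. Sections 6.2.1 and 6.2.2 give a shorter list: IL-6, IL-15, IL-17, GM-CSF and TNFα, plus "anti-inflammatory (IL-4, IL-10 and IL-14) cytokines". TGFbeta1 is on neither.

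**The concern.** Two sections give incompatible accounts of one number. If the group size was arbitrary, a power of 0.8 did not produce it. If 0.8 is meant as a property of 20 per group, nothing shows that it is.

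This matters for interpretation. Section 3.1 asks whether FMT significantly changes the cytokine profile, and section 4.1 plans analysis for statistical significance. With the 0.8 left standing, a null cytokine result could be reported as evidence against a moderate effect from an 80%-powered study. The plan does not support that statement, because the 0.8 belongs to no identified test and its only numeric basis is an analyte the trial does not assay.

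**Working it through.** **Inputs from the documents.** Alpha 0.05 and power 0.8 (section 6.3); 20 per group, 1:1 (synopsis, section 4); 13 cytokine time points, baseline and months 1 to 12 (section 7.0); a 40% change (section 6.3). FMT switches between groups at month 6: "the early intervention will not receive the transplantation anymore and the control group will receive FMT for the remaining 6 months" (section 4.2).

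**Assumptions, because the documents give none.** A moderate effect is 0.5 SD; two-sided testing; one cytokine with no multiplicity correction; correlation r between visits; L, the share of the effect that persists after the last FMT.

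**Step 1: can the plan's own figure be reproduced?** No. Section 6.3 gives no N to check and too few inputs to produce one. The steps below show how far the answer depends on what is missing.

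**Step 2: two groups at one visit.** Noncentral t with noncentrality 0.5 × √(20/2) = 1.58 on 38 df gives power 0.338. Adjusting for baseline at r = 0.5, the residual SD is √(1 − 0.25) = 0.866. The noncentrality becomes 1.58/0.866 = 1.83 on 37 df, and power is 0.428. Solving for 80% power, the detectable difference is 0.91 SD, or 0.79 SD adjusted.

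**Step 3: group-by-visit term of the section 9.3 model.** Under compound symmetry, use a noncentral F on 12 and 38 × 12 = 456 df, with λ = (20/2) × Σ(D_t − mean D)² / (1 − r). D_t is the early-minus-late mean difference. It is 0 at baseline and equals the effect at months 1 to 6. At months 7 to 12 it is L × 0.5 minus the late group's effect. For example, with a constant effect and L = 1, D_t is 0.5 at six visits and 0 at seven. The sum is 6 × 0.25 − 3²/13 = 0.808, so at r = 0.3 λ = 10 × 0.808/0.7 = 11.5 and power is 0.567.

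| Time course | r | L = 0 | L = 0.5 | L = 1 |
|---|---|---|---|---|
| Constant | 0.3 | 0.998 | 0.928 | 0.567 |
| Constant | 0.5 | >0.999 | 0.988 | 0.752 |
| Constant | 0.7 | >0.999 | >0.999 | 0.954 |
| Linear build-up to 0.5 SD | 0.3 | 0.809 | 0.415 | 0.221 |
| Linear build-up to 0.5 SD | 0.5 | 0.939 | 0.580 | 0.312 |
| Linear build-up to 0.5 SD | 0.7 | 0.998 | 0.849 | 0.529 |

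A simulation of 4,000 runs at r = 0.3, L = 1 gave 0.560 (constant) and 0.229 (linear), in agreement.

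**Step 4: baseline to 12 months within patients (section 6.2.3).** Paired t, effect 0.5 SD of the change: noncentrality 0.5 × √40 = 3.16, power 0.87 with 40 patients. With 36 (90% of 40, borrowing the section 5.4 adherence target as a scenario) it is 0.83.

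**Step 5: what is 40% in SD units?** On an assumed log-normal scale, d = |ln(ratio)| / √ln(1 + CV²). The direction of change is not stated, so both are shown.

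| Assumed CV | 40% increase, ln 1.4 = 0.336 | 40% decrease, ln 0.6 = −0.511 |
|---|---|---|
| 40% | 0.87 SD | 1.33 SD |
| 50% | 0.71 SD | 1.08 SD |
| 75% | 0.50 SD | 0.77 SD |
| 100% | 0.40 SD | 0.61 SD |

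A 40% change equals 0.5 SD at a CV of about 76% for an increase and about 136% for a decrease. Without a CV, the 40% and the moderate effect cannot be checked against each other.

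**The case against.** The best defence is that section 9.1 openly calls this an exploratory proof of concept, for which a feasibility sample is acceptable. Nothing has been miscalculated, and section 6.2.3 describes a comparison for which 0.8 at a moderate effect is attainable (0.87 with 40 patients). Section 6.3's talk of a change in cytokine levels even fits that reading. Most of this stands. It is why n=40 need not change and why the problem is one of inconsistency and reporting. It does not rescue the 0.8, because section 6.3 does not point to that comparison, and the 0.87 depends on an assumed paired effect. That comparison also has no concurrent control, and at month 12 the early group is months past its last FMT.

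Two stronger readings are tempting:

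- **That the trial is underpowered.** A reader might infer this from the 34%. That figure belongs to a single-visit test that neither section 9.3 nor section 6.2.3 plans. The planned analyses span values on both sides of 0.8.
- **That dropout will cut the groups to 18.** Section 5.4's 90% is an adherence target, not a forecast of loss. The synopsis says "We may screen up to an extra 10 patients to compensate for possible drop outs", and section 9.7 counts a patient as evaluable after one week of treatment. Eighteen per group (0.9 × 20) is only a scenario.

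The citation is a small matter. The list ends at entry 71, and the later citations run two ahead: section 6.2.3's 72 corresponds to entry 70. So 73 points to entry 71, a vitamin D cytokine study in MS. The source is there under the wrong number.

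**Conclusion.** The point holds as a contradiction and an unsupported claim. Section 6.3 asserts 80% power for a moderate effect without the inputs that would give it meaning, and section 9.1 says n was not derived. The only numeric planning effect is exemplified by an unmeasured analyte, and no SD or CV converts it to an effect size.

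For the same nominal 0.5 SD, power runs from 22% to nearly 100% across the section 9.3 scenarios, with 34% (43% baseline-adjusted) for a single visit and 87% for the within-patient comparison. The 0.5 SD in the paired case is measured in SDs of the change, so it is not the same quantity as in the other two. All these values rest on the assumed effect, correlation, time course, persistence and single-cytokine testing. They show that the power is unspecified, not that it is low. The stated 0.8 should not be used to interpret a positive or a null result. This should be corrected, but it does not affect trial conduct.

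**What to change.** Keep n=40. Delete the power and moderate-effect sentences and the TGFbeta1 basis from section 6.3, and merge sections 6.3 and 9.1 into one statement, for example: *The sample size of 20 per group was chosen for feasibility and not from a power calculation.* That alone removes the contradiction.

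Any figure placed beside it must name its analysis and assumptions. There are two acceptable forms:

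- **A power or detectable effect for a planned analysis.** This is either a named term of the section 9.3 model or the within-patient comparison of section 6.2.3, with the assumed correlation and the assumed persistence after the last FMT stated.
- **A figure labelled as orientation only.** For example: *For the randomised contrast on one cytokine at one visit before the late group's first FMT, two-sided 0.05 and no multiplicity correction, 20 evaluable patients per group give 80% power for a difference of 0.91 SD, or 0.79 SD baseline-adjusted at an assumed correlation of 0.5.*

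If the vitamin D study is still cited, correct reference 73 to 71.

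The cost is wording only, with no extra patients, visits or assays. The downside is that the stated figure becomes less favourable: a feasibility statement, or a detectable difference of 0.91 SD, replaces 0.8 power for a moderate effect.
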